4.1.5 Organ Function Requirements

4.1.5.1 Adequate Renal Function Defined as:

- Creatinine clearance or radioisotope GFR $\geq 60\text{ml/min}/1.73\text{ m}^2$ or
- A serum creatinine based on age/gender as follows:

Age	Maximum Serum Creatinine (mg/dL)	
	Male	Female

THIS PROTOCOL IS FOR RESEARCH PURPOSES ONLY, SEE PAGE 1 FOR USAGE POLICY

1 month to < 6 months	0.4	0.4
6 months to < 1 year	0.5	0.5
1 to < 2 years	0.6	0.6
2 to < 6 years	0.8	0.8
6 to < 10 years	1	1
10 to < 13 years	1.2	1.2
13 to < 16 years	1.5	1.4
≥ 16 years	1.7	1.4

The threshold creatinine values in this Table were derived from the Schwartz formula for estimating GFR (Schwartz et al. J. Peds, 106:522, 1985) utilizing child length and stature data published by the CDC.

4.1.5.2 Adequate Liver Function Defined as:

- Bilirubin (sum of conjugated + unconjugated) \leq upper limit of normal (ULN) for age.
- Alanine aminotransferase (ALT) and aspartate aminotransferase (AST) $\leq 2.5 \times$ ULN. For the purpose of this study, the ULN for SGPT is 45 U/L.

4.1.5.3 Adequate Cardiac Function Defined As:

- Shortening fraction of $\geq 27\%$ by echocardiogram, or
- Ejection fraction of $\geq 50\%$ by echocardiogram or radionuclide angiogram
- No ventricular or supraventricular arrhythmia on EKG
- Prolonged rate corrected QT (QTc) interval < 500 msec

4.1.5.4 Adequate Pulmonary Function Defined As:

- Pulse oximetry $> 94\%$ on room air if there is clinical indication for determination (e.g. dyspnea at rest)

4.1.5.5 Adequate Coagulation Defined As:

- INR ≤ 1.5

4.1.5.6 Adequate Bone Marrow Function Defined As:

- Hemoglobin > 8.0 g/dL (may receive RBC transfusions)

4.1.6 Informed Consent: All patients and/or their parents or legally authorized representatives must sign a written informed consent. Assent, when appropriate, will be obtained according to institutional guidelines.

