5.4.2 Intra-Patient Escalation

Intra-patient dose escalation is not allowed.

5.5 **Grading of Adverse Events**

Adverse events (toxicities) will be graded according to the NCI Common Terminology Criteria for Adverse Events (CTCAE) version 5.0. All appropriate treatment areas should have access to a copy of the CTCAE version 5.0. A copy of the CTCAE version 5.0 can be downloaded from the CTEP website (http://ctep.cancer.gov/protocolDevelopment/electronic_applications/ctc.htm). Any suspected or confirmed dose-limiting toxicity should be reported immediately (within 24 hours) to the Study Chair.

5.6 **Definition of Dose-Limiting Toxicity (DLT)**

DLT will be defined as any of the following events that are possibly, probably or definitely attributable to protocol therapy. The DLT observation period for the purposes of dose-confirmation will be the first cycle of therapy.

Dose limiting hematological and non-hematological toxicities are defined differently.

5.6.1 Non-hematological dose-limiting toxicity:

5.6.1.1 All Grade 3 or greater non-hematological toxicity not clearly related to the underlying disease and attributable to protocol therapy will be considered a DLT except:

- Grade 3 or 4 elevation of ALT/AST that returns to Grade ≤ 1 within 14 days. NOTE: For the purposes of this study the ULN for ALT is defined as 45 U/L regardless of baseline and for AST is defined as 50 U/L regardless of baseline. See [Appendix III](#) for values that represent thresholds between CTCAE grades.

THIS PROTOCOL IS FOR RESEARCH PURPOSES ONLY, SEE PAGE 1 FOR USAGE POLICY

- Grade 3 or 4 electrolyte abnormalities that resolve, with or without supplementation intervention, to \leq Grade 2 within 72 hours. Electrolyte supplementation is encouraged.
- Grade 3 arthralgia/myalgia that returns to Grade \leq 2 within 5 days on analgesics
- Grade 3 or 4 fever, febrile neutropenia, or infection with or without hospitalization
- Grade 3 tumor lysis syndrome
- Alopecia
- Grade 3 maculo-papular or morbilliform rash that resolves to \leq Grade 2 within 7 days
- Grade 3 mucositis that resolves (with or without supportive care) to \leq Grade 2 within 14 days
- Grade 3 fatigue or anorexia responsive to supportive care within 7 days
- Grade 3 nausea, vomiting, and/or diarrhea responsive to supportive care within 72 hours
- Early intervention with TPN or enteral tube feeding for anorexia, nausea, or concern for poor nutritional status

5.6.2 Hematological dose-limiting toxicity:

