6.2 Dose Modifications for Non-Hematological Toxicity

6.2.1 Patients will have ALT/AST/bilirubin evaluated prior to each planned dose of MLN4924 (pevonedistat) in order to determine whether the scheduled dose

should be administered. It is anticipated that ALT and AST may be elevated for approximately 48 hours following the end of the 1st MLN4924 (pevonedistat) infusion.

NOTE: See [Appendix III](#) for toxicity grading table.

If a patient experiences > Grade 3 elevation of ALT/AST on or after Cycle 1, Day 1 then the Cycle 1, Day 3 MLN4924 (pevonedistat) dose should not be given. If ALT/AST returns to \leq Grade 1 or baseline values by Day 5 then the patient should receive their Day 5 MLN4924 (pevonedistat) dose and this will not be considered a DLT. If ALT/AST does not return to \leq Grade 1 or baseline values by Day 5 then MLN4924 (pevonedistat) should be held and this will be considered a DLT. Persistent elevations of ALT/AST > Grade 2 beyond 2 days between any other doses after Cycle 1, Day 1 will be considered a DLT.

6.2.2 Patients who experience a dose limiting toxicity during cycle 1 that resolves to baseline or < Grade 1 at the time of next cycle can proceed with the next cycle at dose level -1.

6.3 **Modifications and Supportive Care Recommendations for Toxicity Related to Protocol Therapy (Cycle 1 and Cycle 2)**

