If a patient experiences \geq Grade 3 elevation of ALT/AST/bilirubin that does not return to \leq Grade 1 or baseline prior to the next dose of MLN4924 (pevonedistat), the dose will be held and this will be considered a DLT. However, patients can still receive azacitidine as scheduled and can receive subsequent fludarabine and cytarabine if ALT \geq Grade 3 after discussion with study chair. NOTE: See [Appendix III](#) for values that represent thresholds between CTCAE grades.

Patients who experience a dose limiting toxicity during cycle 1 that resolves to baseline or \leq Grade 1 at the time of next cycle can proceed with the next cycle at dose level -1.

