APPENDIX III: TOXICITY-SPECIFIC GRADING**Bilirubin**

Grade 1:	> ULN - \leq 1.5 x ULN
Grade 2:	> 1.5 x ULN – 3.0 x ULN
Grade 3:	> 3.0 x ULN – 10.0 x ULN
Grade 4:	> 10.0 x ULN

ALT: For the purpose of this study, the ULN for SGPT is 45 U/L regardless of baseline.

Grade 1:	> 45 U/L - \leq 135 U/L
Grade 2:	136 U/L – 225 U/L
Grade 3:	226 U/L – 900 U/L
Grade 4:	> 900 U/L

AST: For the purpose of this study, the ULN for SGOT is 50 U/L regardless of baseline.

Grade 1:	> 50 U/L - \leq 150 U/L
Grade 2:	151 U/L – 250 U/L
Grade 3:	251 U/L – 1000 U/L
Grade 4:	> 1000 U/L

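### Section 4.1.5.2 states no AST upper limit of normal, though grading fixes it at 50 U/L; with a local limit above 60 U/L, returning to baseline would not meet the 5.6.1.1 DLT exemption

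*Combined protocol and SAP*

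**What the plan says.** **Entry.** Section 4.1.5.2 names both enzymes, "Alanine aminotransferase (ALT) and aspartate aminotransferase (AST"), and caps them at 2.5 × ULN. It then defines one ULN only: "For the purpose of this study, the ULN for SGPT is 45 U/L". It gives no AST value, does not mention a local laboratory and does not point to Appendix III. The preface to Section 4.0 says that the criteria are to be read literally and cannot be waived.

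**Grading.** Section 5.6.1.1 repeats the ALT value and adds that the ULN "for AST is defined as 50 U/L regardless of baseline". Appendix III says the same: "For the purpose of this study, the ULN for SGOT is 50 U/L regardless of baseline". Its AST grades are Grade 1 up to 150 U/L, Grade 2 from 151 to 250 U/L, Grade 3 from 251 to 1000 U/L, and Grade 4 above that.

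**When a transaminase rise is not a DLT.**
- Section 5.6.1.1 exempts a "Grade 3 or 4 elevation of ALT/AST that returns to Grade" 1 or lower within 14 days. It offers no baseline alternative.
- Section 6.2.1 covers a rise on or after Cycle 1 Day 1. It accepts a return to Grade 1 or lower "or baseline values by Day 5 then the patient should receive their Day 5" pevonedistat "dose and this will not be considered a DLT".
- Section 6.3.5 counts a DLT when a rise of Grade 3 or more has not come back to Grade 1 or lower "or baseline prior to the next dose of MLN4924".

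**Decision rule.** Under Section 11.3, Dose Level 1 becomes the recommended phase 2 dose if at most one of up to six evaluable patients has a DLT.

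**The concern.** Entry and grading should be measured against the same ULN, as they are for ALT. For AST the entry section is silent, and a site reading it literally may turn to its own reference range. If that range is high enough, a patient starts the trial already above study Grade 1. The 5.6.1.1 exemption then asks that patient to end up better than at entry, while two parts of Section 6 ask only for a return to entry level.

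The same event could therefore be a DLT under one section and not under another. The DLT count decides the recommended phase 2 dose, and transaminase elevation is a foreseeable event here. Section 6.2.1 anticipates about 48 hours of elevation after the first infusion. In the adult azacitidine combination study described in Section 2.3.1, three of the four patients with DLTs had raised AST and ALT.

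**Working it through.** **1. Reproduce Appendix III.** The printed limits fit 3×, 5× and 20× the fixed ULN (multiples inferred from the table).

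| | ULN (U/L) | 3× (top of Grade 1) | 5× (top of Grade 2) | 20× (top of Grade 3) |
|---|---|---|---|---|
| ALT | 45 | 135 | 225 | 900 |
| AST | 50 | 150 | 250 | 1000 |

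All six values match.

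**2. Entry limit with a fixed ULN.** Entry limit = 2.5 × ULN.
- ALT: 2.5 × 45 = 112.5 U/L, below 135, so every entrant qualifies at Grade 1 or lower.
- AST, if 50 U/L applied at entry: 2.5 × 50 = 125 U/L, below 150, so the same holds.

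**3. Entry limit with a local AST ULN.** The documents give no local range, so the ULNs below are assumptions.

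| Assumed local AST ULN (U/L) | Entry limit (U/L) | Study grade at that limit |
|---|---|---|
| 40 | 100 | 1 |
| 50 | 125 | 1 |
| 60 | 150 | 1 |
| 65 | 162.5 | 2 |
| 80 | 200 | 2 |
| 100 | 250 | 2 |

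The break-even is 150 / 2.5 = 60 U/L. To admit a whole-number value of 151 U/L, the local ULN must be at least 151 / 2.5 = 60.4 U/L.

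**4. Classify one patient under each section.** Assume a local ULN of 65 U/L. The patient enters at 160 U/L (Grade 2), has an attributable rise after the first pevonedistat dose, is back at 160 U/L before the next dose, and stays there through 14 days.

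| Peak AST | 5.6.1.1 | 6.2.1 | 6.3.5 |
|---|---|---|---|
| 251–1000 U/L (Grade 3) | DLT, because 160 > 150 | Trigger is printed as above Grade 3, so literally not reached; if Grade 3 is meant to be included, not a DLT when back by Day 5 | Not a DLT, by implication |
| Above 1000 U/L (Grade 4) | DLT, because 160 > 150 | Expressly not a DLT when back by Day 5 | Not a DLT, by implication |

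Section 5.6.1.1 therefore disagrees with 6.3.5 for either peak. It disagrees with 6.2.1 for Grade 4 as printed, and for Grade 3 as well if that trigger is meant to match 6.3.5.

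**5. Effect on the six-patient rule.** Dose Level 1 is rejected at two or more DLTs. Let p be the true DLT rate (assumed), with six evaluable, independent patients.
- No such case: P(≥2 of 6) = 1 − (1−p)^6 − 6p(1−p)^5.
- One patient already counted through this gap: P(≥1 of the other 5) = 1 − (1−p)^5.

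| p | No such case | One already counted |
|---|---|---|
| 10% | 0.11 | 0.41 |
| 20% | 0.34 | 0.67 |
| 30% | 0.58 | 0.83 |

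The last column is conditional on a case having occurred. It says nothing about how often one will.

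**The case against.** The strongest reply is that the plan already answers the question. Section 5.6.1.1 and Appendix III present the 50 U/L as a definition for the study, not only for grading. Carried back to 4.1.5.2, that definition caps entry at 125 U/L and nobody enters at Grade 2. This reading is reasonable and may be what was intended. It does not settle the matter, because 4.1.5.2 repeats the study-wide definition for ALT and leaves out AST, and the criteria are to be read literally.

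The second reply is that the chain of events is long:
- the site must use a local AST ULN above 60 U/L;
- the patient must enter with AST above 150 U/L while ALT is at most 112.5 U/L and bilirubin at most the ULN, which is close to an isolated AST elevation;
- AST must rise to at least 251 U/L, attributable to protocol therapy;
- AST must return to baseline yet stay above 150 U/L for 14 days.

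This stands, and it limits how often the problem can arise. The adult data point the same way: at 20 mg/m², Section 2.3.1 reports two patients with transaminase DLTs out of 55 treated, both transient.

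The third reply is that 6.2.1 already removes the DLT for a return to baseline by Day 5. That is correct for the cases it covers, but 5.6.1.1 is the section that defines a DLT and it contains no such clause. The conflict is therefore still open.

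**Conclusion.** The point holds as a drafting gap with a conditional effect on the DLT count. The omission of an AST ULN from 4.1.5.2, and the difference between 5.6.1.1 and Section 6 over baseline, are plain in the text. Entry at Grade 2 depends on a site using a local AST ULN above 60 U/L, which the documents neither show nor exclude. At 60 U/L or below the gap has no effect.

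A reader might infer three stronger things, none of which the documents support:
- *That the plan assigns the AST limit to the local laboratory.* It does not; 4.1.5.2 is silent.
- *That the resulting DLT would come from the reference range and not from treatment.* Grade 2 at entry is not a DLT. A new rise to at least 251 U/L, judged attributable to protocol therapy, must come first. The reference range affects only whether the exemption can be met afterwards.
- *That one such case would reject Dose Level 1.* Section 11.3 tolerates one DLT in six, so a second is needed. What is lost is the single allowance.

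Such cases are probably uncommon. The change is worth making because it is cheap and bears on the count that sets the recommended phase 2 dose.

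**What to change.** 1. State in 4.1.5.2 which AST ULN applies at entry. If it is the 50 U/L already defined in 5.6.1.1 and Appendix III, one added sentence sets the entry limit at 125 U/L, and every entrant qualifies at Grade 1 or lower, as for ALT. The cost is that some patients at sites with a local ULN above 50 U/L become ineligible. These include patients between 126 and 150 U/L, who are Grade 1 and could have met the exemption. The documents do not allow their number to be estimated.

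2. Reconcile the ALT/AST return criterion across 5.6.1.1, 6.2.1 and 6.3.5 so that each event has one DLT classification. The sections differ on whether baseline is accepted, on the time allowed (14 days, Day 5, or the next dose) and on the grade that triggers the rule (above Grade 3 in 6.2.1, Grade 3 or more in 6.3.5). Which rule is right is for the sponsor to decide. The cost is a few sentences of text.

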4.2 Exclusion Criteria

4.2.1 Pregnancy or Breast-Feeding

Pregnant or breast-feeding women will not be entered on this study due to risks of fetal and teratogenic adverse events as seen in animal/human studies, *OR* because there is yet no available information regarding human fetal or teratogenic toxicities. Pregnancy tests must be obtained in girls who are post-menarchal. Males or females of reproductive potential may not participate unless they have agreed to use 1 highly effective and 1 additional effective (barrier) method of contraception at the same time for the duration of study therapy and for 4 months after the completion of MLN4924 (pevonedistat) administration. True abstinence,

when this is in line with the preferred and usual lifestyle of the subject, is acceptable. Periodic abstinence (e.g., calendar, ovulation, symptothermal, post-ovulation methods), withdrawal, spermicides only, and lactational amenorrhea are not acceptable methods of contraception.

4.2.2 Concomitant Medications

4.2.2.1 Investigational Drugs: Patients who are currently receiving another investigational drug are not eligible.

4.2.2.2 Anti-cancer Agents: Patients who are currently receiving other anti-cancer agents are not eligible [except hydroxyurea, which may be continued until 24 hours prior to start of protocol therapy].

4.2.2.3 Anti-GVHD agents post-transplant:

Patients who are receiving cyclosporine, tacrolimus or other systemic agents to prevent graft-versus-host disease post bone marrow transplant are not eligible for this trial. Topical immunosuppressive agents (e.g. topical steroids) are allowed. Physiologic replacement of hydrocortisone is allowed.

4.2.2.4 Patients who are taking drugs that are strong CYP3A4 inducers and cannot be switched to alternative drugs 14 days prior to enrollment are not eligible. Strong inducers of CYP3A4 are not permitted during the study. See [Appendix IX](#) for more details.

4.2.3 Patients with known hepatitis B surface antigen seropositive or known or suspected active hepatitis C infection are not eligible. **NOTE:** Patients who have isolated positive hepatitis B core antibody (i.e. in the setting of negative hepatitis B surface antigen and negative hepatitis B surface antibody) must have an undetectable hepatitis B viral load. Patients who have positive hepatitis C antibody may be included if they have an undetectable hepatitis C viral load.

4.2.4 Patients with known hepatic cirrhosis or severe pre-existing hepatic impairment are not eligible.

4.2.5 Patients with uncontrolled high blood pressure (i.e., $\geq 99\%$ for age, see [Appendix XI](#)) are not eligible.

4.2.6 Patients with any of the following diagnoses:

- Acute promyelocytic leukemia
- Down syndrome
- Juvenile myelomonocytic leukemia

4.2.7 Infection: Patients who have a documented active uncontrolled infection are not eligible.

4.2.8 History of allergic reactions attributed to compounds of similar chemical or biologic composition as the study agent.

THIS PROTOCOL IS FOR RESEARCH PURPOSES ONLY, SEE PAGE 1 FOR USAGE POLICY

4.2.9 Patients with HIV are not eligible unless they meet all of the following criteria:

- CD4 count > 350 cell/mm³
- Undetectable viral load
- Maintained on modern therapeutic regimens utilizing non-CYP-interactive agents
- No history of AIDS-defining opportunistic infections

4.2.10 Female patients who intend to donate eggs (ova) during the course of this study or 4 months after receiving their last dose of study drug(s) are not eligible.

4.2.11 Male patients who intend to donate sperm during the course of this study or 4 months after receiving their last dose of study drug(s) are not eligible.

5.0 TREATMENT PROGRAM

5.1 Overview of Treatment Plan

The primary purpose of this feasibility study is to evaluate the safety and toxicity profile of MLN4924 (pevoneditstat) in combination with azacitidine, fludarabine, and cytarabine in children with relapsed or refractory AML or MDS and to recommend a phase 2 dose for use in further studies. A rolling 6 design will be utilized. Patients will receive 1 dose of intrathecal cytarabine with a diagnostic lumbar puncture to be performed prior to the start of each cycle of therapy.

For patients ≥ 1 year of age, MLN4924 (pevoneditstat) will be administered at 20 mg/m²/dose intravenously (IV) on days 1, 3 and 5. Azacitidine will be administered at 75 mg/m²/dose IV once daily on days 1-5. On days 1, 3, and 5 when both drugs are administered, azacitidine will be administered first followed by MLN4924 (pevoneditstat) infusion. The infusion of MLN4924 (pevoneditstat) will begin between 30-60 minutes after completion of IV azacitidine. Following completion of azacitidine and MLN4924 (pevoneditstat), fludarabine 30 mg/m²/dose IV once daily and cytarabine 2000 mg/m²/dose IV once daily will be administered on days 6-10. Cytarabine infusion will begin 4 hours after the start of fludarabine.

For patients < 1 year of age, MLN4924 (pevoneditstat) will be administered at 15 mg/m²/dose intravenously (IV) on days 1, 3, and 5. Azacitidine will be administered at 2.5 mg/kg/dose IV once daily on days 1-5. On days 1, 3, and 5 when both drugs are administered, azacitidine will be administered first followed by MLN4924 (pevoneditstat) infusion. The infusion of MLN4924 (pevoneditstat) will begin between 30-60 minutes after completion of IV azacitidine. Following completion of azacitidine and MLN4924 (pevoneditstat), fludarabine 1 mg/kg/dose IV once daily and cytarabine 67 mg/kg/dose IV once daily will be administered on days 6-10. Cytarabine infusion will begin 4 hours after the start of fludarabine.

Patients without additional evidence of CNS disease (CNS1) do not require additional CNS-directed therapy during the cycles. Patients with blasts detected in the CNS (CNS2/3) will receive additional intrathecal chemotherapy with IT cytarabine or IT triple therapy (cytarabine, hydrocortisone, methotrexate) per institutional standards at a schedule of 2x/weekly until the CNS is clear of blasts on 2 consecutive LPs, with a minimum of 4 IT cytarabine or IT triple (ITT) doses administered.

NOTE: Central venous access in the form of a double lumen Broviac or Hickman is highly recommended.

	Day 0	1	2	3	4	5	6	7	8	9	10	11-34	35
IT Cytarabine (all patients)	X												
Azacitidine		X	X	X	X	X							
MLN4924 (Pevonedistat)		X		X		X							
Fludarabine							X	X	X	X	X		
Cytarabine							X	X	X	X	X		
IT Cytarabine OR ITT* (CNS2/3)									X*			X*	

*For patients with CNS 2/3 status, IT cytarabine or ITT should be administered 2x/weekly until the CNS is clear of blasts on 2 consecutive LPs, with a minimum of 4 IT cytarabine/IT triple doses administered. This should begin on Day 8 and should be repeated 2x/weekly with not less than 3 days between doses, thus any necessary subsequent doses should be given starting on Day 11. Days of therapy may vary depending on scheduling.

A cycle of therapy is considered to be 35 days. A cycle may be repeated for a total of 2 cycles, up to a total duration of therapy of approximately 4 months.

Drug doses of MLN4924 (pevonedistat), azacitidine, fludarabine, and cytarabine should be adjusted based on the BSA calculated from height and weight measured within 7 days prior to the beginning of each cycle. Drug doses of intrathecal cytarabine and intrathecal triples should be based on the age at the time of administration.

See [Appendix VIII](#) for Therapy Delivery Maps for each cycle.

5.2 Treatment Details (Cycles 1 & 2)

Intrathecal cytarabine: IT

All patients will receive 1 dose of IT cytarabine using age-based dosing below at the time of diagnostic lumbar puncture, or on Day 0 of each cycle. Patients may be given intrathecal cytarabine up to 1 week prior to Day 1, but at least 24 hours prior to the start of MLN4924 (pevonedistat) and azacitidine on Day 1. If IT cytarabine is given prior to enrollment, a separate institutional consent must be obtained.

Age-based dosing:

Age (yrs)	Dose
< 1	20 mg
1-1.99	30 mg
2-2.99	50 mg
≥ 3	70 mg

Triples (Methotrexate/Hydrocortisone/Cytarabine): IT

For CNS2/3 patients only. IT triples may be given instead of IT cytarabine for CNS2/3 patients in Cycle 1 after the Day 0 IT cytarabine dose per the details described below.

Age-based dosing:

Age (yrs)	Dose
<1	MTX: 7.5 mg, HC: 7.5 mg, ARAC: 15 mg
1-1.99	MTX: 8 mg, HC: 8 mg, ARAC: 16 mg
2-2.99	MTX: 10 mg, HC: 10 mg, ARAC: 20 mg
3-8.99	MTX: 12 mg, HC: 12 mg, ARAC: 24 mg
≥ 9	MTX: 15 mg, HC: 15 mg, ARAC: 30 mg

For CNS2 or CNS3 patients:

Patients with CNS2 or CNS3 involvement at screening will receive additional intrathecal chemotherapy with IT cytarabine or IT triples (doses as above) at a twice weekly schedule until the CNS is clear of blasts on 2 consecutive LPs. The administration of IT cytarabine vs IT triples is up to the treating physician's discretion. A minimum of 4 and a maximum of 6 intrathecal treatments may be given. This count includes the pre-study/Day 0 dose. Subjects who have persistent CNS disease despite 6 doses of IT cytarabine or IT triples will be off study treatment and considered treatment failures (See [Section 12.2.5](#)). See [Section 12.3](#) for definitions of CSF involvement.

Azacitidine: IV over 15 minutes once daily

Days: 1-5

Dose: Age based dosing

Age	Dose
<1 year	2.5 mg/kg/dose
≥ 1 year	75 mg/m ² /dose

Note: infusion must be completed within 1 hour of vial reconstitution

On Days 1, 3, and 5 azacitidine will be given 30-60 minutes before MLN4924 (pevoneditat) infusion. See details of the timing below.

MLN4924 (Pevonedistat)*: IV over 60 minutes

Days: 1, 3, and 5

Starting dose: 20 mg/m² for patients ≥ 1 year of age; 15 mg/m² for patients < 1 year of age (Dose Level 1). See Dosing Schema in [Section 5.4](#).***NOTE:** Give MLN4924 (pevoneditat) 30 – 60 minutes after the completion of the azacitidine infusion. If MLN4924 (pevoneditat) dosing is delayed, a minimum of 1 full calendar day between any 2 doses should be maintained.**Fludarabine: IV over 30 minutes once daily**

Days: 6-10

Dose: Age based dosing

Age	Dose
< 1 year	1 mg/kg/dose
≥ 1 year	30 mg/m ² /dose

High Dose Cytarabine: IV infusion over 1-3 hours once daily

Days: 6-10

Dose: Age based dosing (begin 4 hours after start of fludarabine)

Age	Dose
< 1 year	67 mg/kg/dose
≥ 1 year	2000 mg/m ² /dose

Please note: Following/during high-dose cytarabine, chemical conjunctivitis may occur. Administer steroid eye drops (0.1% dexamethasone or 1% prednisolone ophthalmic solution), 2 drops to each eye every 6 hours, beginning immediately before the first dose and continuing for 24 hours after the last dose. If patient does not tolerate steroid eye drops, artificial tears may be administered on an every 2-4 hour schedule.

See the Chemotherapy Administration Guidelines (CAG) on the COG website at: https://cogmembers.org/_files/disc/Pharmacy/ChemoAdminGuidelines.pdf for special precautions and suggestions for patient monitoring during the infusion. As applicable, also see the CAG for suggestions on hydration, or hydrate according to institutional guidelines.

5.3**Criteria for Starting Cycle 2**

Patients may proceed to cycle 2 following completion of cycle 1 disease assessment if stable or greater response and if non-hematologic toxicities probably or definitely related to MLN4924 (pevoneditstat) recover to \leq grade 2. Bilirubin, ALT, and AST must be \leq Grade 1 or at the patient's baseline values prior to starting Cycle 2.

NOTE: See [Appendix III](#) for Toxicity Specific Grading.

- Patients will have disease assessment on Day 36-39 of Cycle 1. If a bone marrow aspirate cannot be evaluated (dry tap, no spicules), a follow-up bone marrow aspirate and biopsy must be performed within 2 weeks to assess cellularity and response.
- If aspirate and/or biopsy results indicate hypocellular marrow (<10% cellularity on biopsy), then continue to repeat bone marrow aspirate and/or biopsy not less than once every 14 days until response can be assessed.
- If count recovery is noted within 14 days of an unevaluable marrow, there is no need to repeat the marrow to confirm response.
- If the patient meets criteria for CR, CRp, or CRi after Cycle 1 then the patient can proceed to Cycle 2 (See [Section 12.2](#) for definitions of response)
- If the bone marrow aspirate and/or biopsy performed after Cycle 1 reveals $\geq 5\%$ but $\leq 25\%$ blasts, then the patient should proceed to Cycle 2 of chemotherapy

5.4**Dosing Schema****5.4.1 Dose Confirmation Schema**

The starting dose will be 20 mg/m² for patients ≥ 1 year of age (Dose Level 1) with dose levels for subsequent groups of patients as follows:

Dose Level	MLN4924 (Pevonedistat) Dose (mg/m ²)
-1	15 mg/m ²
1*	20 mg/m²

* Starting Dose Level

The starting dose will be 15 mg/m² for patients < 1 year of age (Dose Level 1) with dose levels for subsequent groups of patients as follows:

Dose Level	MLN4924 (Pevonedistat) Dose (mg/m ²)
-1	10 mg/m ²
1*	15 mg/m²

* Starting Dose Level

There will be no escalations beyond Dose Level 1 (20 mg/m²), as adult studies examining doses higher than 20 mg/m² observed excess toxicity without any apparent disease benefit and no significant differences in pharmacokinetic parameters to suggest significant increase in efficacy.²⁴

If the maximally tolerated dose (MTD) has been exceeded at the first dose level, then the subsequent cohort of patients will be treated at Dose Level -1. If Dose Level -1 is not well tolerated, further de-escalation will not occur. The study will be closed to accrual.

